7.2.1 AE Documentation

A laboratory test abnormality considered clinically relevant (e.g., causing the subject to withdraw from the study, requiring treatment or causing apparent clinical

manifestations, result in a delay or dose modification of study treatment, or judged relevant by the investigator), should be reported as an adverse event.

The investigator or sub-investigator (treating physician if applicable) will document the following for all adverse events (both serious and non-serious):

- Event term- according to the NCI Common Terminology Criteria for Adverse Events (CTCAE) version 5. The CTCAE current version is available at http://ctep.cancer.gov/reporting/ctc.html
- Description of the event
- Date of onset and resolution
- Expectedness of the toxicity
 - Expected events are those that have been previously identified as resulting from administration of the agent. An adverse event is considered unexpected, for expedited reporting purposes only, when either the type of event or the severity of the event is not listed in:
 - the current known adverse events listed in this protocol;
 - the drug package insert; and/or
 - the current Investigator's Brochure
- Grade of toxicity
 - Attribution of relatedness to the investigational agent- (this must be assigned by an Investigator, sub-investigator, or treating physician)
 - Attribution categories are as follows:
 - Definite: The AE is clearly related to the study treatment.
 - Probable: The AE is likely related to the study treatment.
 - Possible: The AE may be related to the study treatment.
 - Unlikely: The AE is doubtfully related to the study treatment.
 - Unrelated: The AE is clearly NOT related to the study treatment.
- Action taken as a result of the event, including but not limited to; no changes, dose interrupted, reduced, discontinued, etc. or action taken with regard to the event, i.e. no action, received conmed or other intervention, etc.
- Outcome of event

Source documentation must be available to support all AEs.

7.2.2 Duration of AE monitoring

All patients experiencing an adverse event, regardless of its relationship to study drug, will be monitored until:

- the AE resolves or the symptoms or signs that constitute the AE return to baseline
- any abnormal laboratory value deemed an AE as per section 7.1.1.1, has returned to baseline
- there is a satisfactory explanation other than the study drug for the changes observed
- death, or
- until 30 days following last dose of study drug or until initiation of a new anticancer therapy (whichever occurs first)

7.2.3 Pembrolizumab

As pembrolizumab is FDA-approved for this indication and used in accordance with the package insert, only events determined to be unexpected and at least possibly related to pembrolizumab will be recorded in the eCRF.

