With the development of new chemotherapies or targeted agents which are potentially more effective and less toxic, many patients can still maintain a good general condition after failing second-line therapies. According to previous studies, around 20–90% patients were able to continue active third-line or further lines of treatment. Established third-line therapies include chemotherapies: irinotecan, taxane and TAS-102, tyrosine kinase inhibitors: apatinib and regorafenib, and immune-checkpoint inhibitors (CPIs): nivolumab and pembrolizumab. Given the expanding options for third-line therapies, there is an unmet need for clinicians to individualize treatment.

Pembrolizumab is a humanized anti-PD-1 monoclonal antibody. In the KEYNOTE-059 Cohort 1, a multicenter, open-label, single-arm phase II trial conducted at 67 sites in 17 countries, 259 patients (after failing two or more lines of chemotherapy including cisplatin and 5FU; patients with Her-2 positive tumors must have received treatment with trastuzumab) received a fixed dose of 200mg pembrolizumab in a 3-weekly cycle [12]. Pembrolizumab showed an objective response rate of 11.6% (95% CI 8.0–16.1%), with complete response of 2.3% (95% CI 0.9–5.0%). The response rate was higher in the patients with PD-L1 positive tumors (PD-L1-positive versus PD-L1-negative: 15.5% versus 6.4%). A total of seven (4%) tumors were microsatellite instable (MSI)-high (H) and the response rates were higher, with an overall response rate of 57,1%. Median PFS was 2.0 months and median OS was 5.6 months. Based on this result, the Food and Drug Administration (FDA) has approved pembrolizumab as the third line treatment for PD-L1-positive gastric adenocarcinoma. Adverse events (AE) of any grade was reported in 60.2% of patients receiving pembrolizumab. The most common any-grade AEs were fatigue, pruritis, rash, hypothyroidism, decreased appetite, anemia, nausea, diarrhea and arthralgia. Grade \geq 3 treatment-related AEs occurred in 17.8% patients, with more common AEs including anemia, fatigue and diarrhea. Overall, 17.8% of patients experienced at least one immune-mediated AE of any grade; the most common were hypothyroidism (8.9%), hyperthyroidism (3.5%) and colitis (2.3%).

This study aims to explore the clinical safety and efficacy of combination of Telatinib, a potent oral inhibitor of VEGFR2 tyrosine kinase, and Pembrolizumab within the 3rd line and after treatment of locally advanced and metastatic gastric cancer

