2.4.3 Safety Evaluations

• Incidence and severity of adverse events by CTCAE V5

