5.2.1 Treatment-Related Serious Adverse Events

Non-hematologic serious adverse events, graded 3 or 4 per CTCAE v5, deemed probably related or related to telatinib (alone or in combination), occurring within the first cycle of treatment, will be monitored throughout the study for safety stopping rules (see Section 9.4). Serious adverse events deemed probably related or related to Keytruda alone will not count toward safety stopping rules.

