7.1.3 Unanticipated Problem Involving Risk to Subjects or Others (UPIRSO)

UPIRSOs include any incident, experience, or outcome that meets all of the following criteria:

- Unexpected (in terms of nature, severity, frequency) given (a) the research procedures that are described in the protocol-related documents, such as the IRB-approved research protocol and informed consent document; and (b) the characteristics of the subject population being studied;
- Related or possibly related to participation in the research (possibly related means there is a reasonable possibility that the incident, experience, or outcome may have been caused by the procedures involved in the research); and
 - Suggests that the research places subjects or others at a greater risk of harm (including physical, psychological, economic, or social harm) than was previously known to an individual or group of individuals (including research subjects, research staff, or others not directly involved in the research).

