7.2 Principal Investigator Responsibilities for Safety Monitoring

The investigator or designee is responsible for ensuring that adverse events (both serious and non-serious) observed by the clinical team or reported by the subject which occur from treatment administration on Cycle 1 Day 1 and until 30 days following the last dose of the study drug or until initiation of a new anticancer therapy (whichever occurs first), are fully recorded in the subject's medical records. Source documentation must be available to support all adverse events.

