9.3.2 Safety Analysis

All subjects who receive at least one dose of telatinib will be included in the safety analysis. The frequencies of AEs by type, body system, severity and relationship to study drug will be summarized. SAEs (if any) will be described in detail.

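### Section 7.2.3 keeps expected pembrolizumab-only events out of the eCRF, while 2.4.3 and 9.3.2 promise adverse-event incidence and frequencies with no such exclusion

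*Combined protocol and SAP*

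**What the plan says.** Section 7.2.3 sets the eCRF rule for pembrolizumab: "only events determined to be unexpected and at least possibly related to pembrolizumab will be recorded in the eCRF". Its stated reason is that the drug is approved for the indication and used according to its label.

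Section 2.4.3 defines the safety evaluation as "Incidence and severity of adverse events by CTCAE V5". Section 9.3.2 covers everyone who takes at least one dose of telatinib and states: "The frequencies of AEs by type, body system, severity and relationship to study drug will be summarized". Neither section sets aside any class of event. Safety is a secondary objective (2.2.4) and is in the study title.

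Other sections bear on what is recorded and where:
- **7.2** requires all AEs from Cycle 1 Day 1 to be in the medical record, until 30 days after the last dose or a new anticancer therapy. It does not mention the eCRF.
- **7.2.1** requires term, grade, attribution and expectedness to be documented for every AE. Attribution is on a single scale, to the investigational agent or study treatment.
- **6.1.6** puts AE severity, outcome, treatment and relationship on the CRF with no pembrolizumab exception. It sits under the screening procedures and refers to section 7.0 for monitoring.
- **5.2.1** says of the stopping rules: "Serious adverse events deemed probably related or related to Keytruda alone will not count toward safety stopping rules".

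**The concern.** The safety summaries are described as AE frequencies in the treated population, but the data-capture rule removes one class of events before any table is made. Nothing in the analysis text tells the reader of the table that this happened. The counts could be taken as the full AE incidence of telatinib plus pembrolizumab when they are not.

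The reason given in 7.2.3 does not remove the difficulty. Approval of pembrolizumab speaks to its known profile, and the rates quoted in 1.1.1 and 1.1.2 come from pembrolizumab given alone. Whether listed toxicities occur at the same rate with a VEGFR2 inhibitor added is part of what a safety summary of the combination should show.

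**Working it through.** The plan states no figure for this loss, so there is none to reproduce. The check is a comparison of the texts, followed by a calculation for scale.

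**Step 1: which events are removed.** 7.2.3 requires two things together: the event is unexpected, and it is at least possibly related to pembrolizumab. An event that is expected, attributed to pembrolizumab and not attributed to telatinib fails the first condition and is not entered. This is the narrow reading. 7.2.3 does not say how to treat an expected event attributed to both drugs.

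**Step 2: whether another rule brings them back.**
- 7.2 and 7.2.1 keep the events in source but do not move them to the eCRF.
- 6.1.6 has two possible readings. If it applies on treatment, it contradicts 7.2.3. If it is confined to baseline, the gap stands. Either way the sections need reconciling.
- 5.2 sends events requiring dose reduction to the CRF, and also the reasons for doses not given per protocol. It does so under telatinib dose modification.
- 5.4 puts concomitant medication on the CRF, but that is not an AE row.
- 10.4 and 10.8 mention a study database in general terms. They do not say that events filtered by 7.2.3 are entered there or added to the tables.

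**Step 3: whether the exclusion is implied in the analysis text.** 5.2.1 shows that the protocol states the exclusion of Keytruda-alone events where it intends one. 2.4.3 and 9.3.2 do not. In 9.3.2, relationship to study drug is a way of classifying AEs, not a limit on which are counted.

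**Step 4: what counts as expected.** Under 7.2.1 the test is whether the event appears in the reference documents, judged by two features: "An adverse event is considered unexpected, for expedited reporting purposes only, when either the type of event or the severity of the event". On that definition a listed event that becomes more frequent remains expected. Frequency enters only the UPIRSO definition in 7.1.3: "Unexpected (in terms of nature, severity, frequency) given (a) the research procedures". 7.2.3 does not say which definition it uses.

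**Step 5: scale.** Inputs: n = 21 gastric patients (Study Schema and 9.1); hypothyroidism 8.9% and hyperthyroidism 3.5% on pembrolizumab alone (1.1.1). Let s be the share of such events judged expected and due to pembrolizumab only. The documents do not give s, so it is shown over its whole range.

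Expected cases = n × p. P(at least one) = 1 − (1 − p)^n. Omitted cases = n × p × s.

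| Event | n × p | P(at least one) | Omitted at s = 0 / 0.5 / 1 |
|---|---|---|---|
| Hypothyroidism | 21 × 0.089 = 1.87 | 1 − 0.911^21 = 0.86 | 0 / 0.93 / 1.87 |
| Hyperthyroidism | 21 × 0.035 = 0.74 | 1 − 0.965^21 = 0.53 | 0 / 0.37 / 0.74 |

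These are monotherapy rates used for scale, not estimates of what this trial will lose.

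**The case against.** The strongest reply is that 7.2.3 is a deliberate, explained choice with little consequence. Every AE is in source with grade, attribution and expectedness. Every SAE reaches the PI within 24 hours whatever its attribution (7.3.1.1), and 9.3.2 describes SAEs in detail. Thyroid function is tested at baseline and in even cycles (6.1.8, 6.2.2, 6.4). The PI reviews data continuously, and DSMC findings are reported every three months (10.5.2). Fatigue, nausea and diarrhea are listed for both drugs, so attribution to pembrolizumab alone is less likely for them, and the thyroid rows are the ones where the filter has most room to act. The numbers are small in any case: the exact 95% interval for 4 of 21 patients runs from 5.4% to 41.9% and contains 8.9%, so even complete recording could not reliably show a moderate rise.

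Most of this stands, and it limits the point. A reader might infer that a rise in pembrolizumab toxicity under the combination would go unseen. The documents do not support that: source records, scheduled thyroid tests and safety review all remain, and s is unknown. Choosing an assumed rise and an assumed omission share that cancel would prove nothing, since the result follows from the choice.

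The reply does not remove the conflict. None of these safeguards is named as a source for the AE tables, and no laboratory summary is promised. Small counts make an undisclosed omission harder to notice. Recording every AE in the eCRF is one remedy and not the only one; stating the exclusion where the tables are defined is the minimum.

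**Conclusion.** The point holds as an inconsistency between the capture rule and the promised safety summaries, and it should be fixed. If the AE tables are built from the eCRF, rows for listed pembrolizumab toxicities may be under-counted, mainly for non-serious events, and a higher frequency under the combination could be partly masked in those tables.

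The loss ranges from zero upward and cannot be narrowed from the documents. On the thyroid rows in the gastric cohort it lies between 0 and about 1.9 cases of hypothyroidism and between 0 and about 0.7 of hyperthyroidism, if the monotherapy rates applied.

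This rests on two assumptions: that the eCRF feeds the tables, and that 6.1.6 does not override 7.2.3 for on-treatment events. The primary PFS analysis is not touched. Nor are the stopping rules, which already set aside Keytruda-alone SAEs.

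**What to change.** Reconcile 2.4.3, 6.1.6, 7.2.1, 7.2.3 and 9.3.2.

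**Preferred.**
- Replace 7.2.3 so that every AE in the 7.2 window is entered in the eCRF whatever its expectedness or attribution.
- Amend 7.2.1 to record relationship to telatinib and relationship to pembrolizumab as two separate items. Its present single scale does not do this, and the drug-specific judgment in 5.2.1 covers only SAEs.
- Make 6.1.6 consistent with the new rule.
- Keep expectedness for expedited reporting only, as 7.2.1 already says.

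The cost is additional eCRF entry and one more attribution field for 21 + 24 = 45 patients. The events are already assessed each cycle and documented in source.

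**If the filter is kept.** 2.4.3 and 9.3.2 should name the data source for the AE tables, state that expected pembrolizumab-only events are excluded, and state that the reported frequencies are not the full AE incidence of the combination. 6.1.6 should carry the same exception, and 7.2.3 should say which definition of unexpected applies. The cost is a few sentences.

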7.3 Safety Reporting Requirements

7.3.1.1 Reporting to the Principal Investigator

The Principal Investigator must be notified by study staff or co-investigators within 24 hours of learning of any serious adverse events, regardless of attribution, occurring during the study or within 30 days of the last administration of the study drug or until initiation of a new anticancer therapy (whichever occurs first).

Contact for Expedited Reporting:

[name], MPH [contact]; [contact]

Alternate Contact for Expedited Reporting:

[name] [contact]; [contact]

7.3.1.2 Reporting to DSMC:

Serious Adverse Events deemed to be related to the protocol and on-study deaths, including death of a research subject unless the death is expected (e.g. due to disease progression) are to be reported to the DSMC within 24 hours of awareness. Hardcopies or electronic versions of the MedWatch Form 3500A (Mandatory Reporting) or a narrative report, along with any other supporting documentation available, should be submitted to the DSMC Coordinator. The DSMC Coordinator will forward the information to the DSMC Chair, and/or medical monitor. The DSMC Chair will review all documentation upon receipt from the DSMC Coordinator and determination of whether the following actions are required: 1) takes action immediately, 2) convenes a special DSMC session (physical or electronic), or 3) defers the action until a regularly scheduled DSMC meeting. Reports to be emailed to the DSMC team at [contact].

7.3.1.3 Reporting to the Institutional Review Board (IRB)

As per the Cedars-Sinai IRB Reporting Possible Unanticipated Problems Involving Risks to Subject or Others (UPIRSO) Policy, the IRB must be notified of all UPIRSOs as soon as possible, but no later than 10 business days from when the study team learned of any of the following events: Any serious event (injuries, side effects, deaths or other problems), which in the opinion of the Principal Investigator was unanticipated, involved risk to subjects or others, and was possibly related to the research procedures.

- Any internal AE, SAE or Research-Related Subject Injury (RRSI), which in the opinion of the Principal Investigator was unanticipated or unexpected, and has a reasonable possibility of relationship to the research.
- Any actionable external SAE, AE, SUSAR, development safety update report (DSUR), or FDA MEDWATCH report deemed to be a UPIRSO. An event is considered "actionable" if it warrants a change to the conduct of the study.
- Any accidental, unintentional protocol or consent/HIPAA related deviation that may impact subjects' rights, safety, or welfare. See section 10.8.3.
- Any planned protocol exception or eligibility waiver. See sections 10.8.2 and 10.8.3.

- Changes to the research or protocol deviations made without prior IRB approval in order to eliminate apparent immediate hazard to a research subject.(Note: These must be reported to the IRB within 5 business days.)
- Problems, events, unanticipated incidental findings, billing problems, or other events, outcomes, or new information related to the research (e.g., publication, safety monitoring report, interim findings, product labeling changes, findings generated from preclinical, animal studies) that may adversely affect the rights, safety, or welfare of the subjects or others, put subjects or others at increased risk, compromise the research data, or require/recommend changes to the study conduct.
- Any new information (e.g., publication, safety monitoring report, updated sponsor safety report), interim result or other finding that indicates an unexpected change to the risk/benefit ratio for the research.
- Breach or potential breach of confidential or sensitive information.
- Subject complaints or concerns that cannot be resolved by the research staff to the subject's satisfaction.
- Incarceration of a subject who is enrolled in a study that is not approved by the IRB to include prisoners.

7.3.1.4 Reporting to the Food and Drug Administration

The sponsor-investigator of the IND, or designee must submit all reported SUSARs to the FDA on FDA Form 3500A (MedWatch).

The sponsor-investigator of the IND must notify the FDA as soon as possible but no later than:

- 7 calendar days after the sponsor-investigator's initial receipt of the information in a written IND safety report of any fatal or life-threatening SUSARs.
- **15 calendar days** after the sponsor-investigator's initial receipt of the information in a written IND safety report of any **non-fatal / non-life-threatening SUSARs**.

Copies of IND Safety Reports will be kept in the Trial Master File in the SOCCI CCTO.

7.3.1.5 Reporting to EOC Pharma

SUSARs reported to the FDA as per Section 7.4.2.4 will be sent to EOC Pharma within 3 days of awareness via the MedWatch FDA Form 3500A, and emailed to [contact].

8.0 CORRELATIVES/SPECIAL STUDIES

The effect of immune modulation will be assessed by inflammatory cytokines in subject plasma samples. Changes in metabolites and inflammatory biomarkers will also be assessed in plasma. Changes in the stool microbiome will be assessed by 16s and/or shotgun metagenomics analysis. Stool metabolites will also be measured by MS-based quantitation. Stool microbiome and metabolites will be compared to samples collected from subjects on SOC Keytruda collected through the GI-Bank protocol (IRB# Pro00054363).

8.1 Plasma and PBMC Collection / Specimen Banking

Immune modulation will be assessed by FACS from PBMCs, inflammatory cytokines and metabolites will be assessed in the plasma.

- A fasting morning research plasma sample will be collected at odd cycles during the study and at the end-of-treatment visit.
- Samples will be processed in the CSMC CCTO lab or Biobank.

• Samples will be stored indefinitely in [name] rental freezer.

8.2 Stool Specimen Collection / Banking

8.2.1 Materials/ Sample Collection

• A research stool sample will be collected at screening/baseline and C3D1. A stool collection kit will be given to the patient during the physical exam, where the patient will be advised to follow the instructions on the kit and bring their sample into laboratory within 4 weeks prior to Cycle1/Day1 or on Cycle 1 Day 1, and at C3D1 (+/- 3 days). Microbiome analysis will be measured from the collection of stool sample.

8.2.2 Process

 Patients will be advised to keep the stool sample frozen until transport to the clinic. Upon receipt of the sample at the investigator site, site personnel should verify that the collection date and subject ID is written on a paper in a biohazard bag with the stool container.

8.2.3 Storage of Stool Sample/ Specimen Banking

- The stool sample will be transported to the CCTO laboratory for short term storage.
- Samples will be stored indefinitely in [name] rental freezer.

9.0 STATISTICAL CONSIDERATIONS

9.1 Sample Size

For the AGC cohort, the median PFS in the KEYNOTE-059 trial (Fuchs et al. 2020) is 2.0 months. Assuming an accrual time of 12 months and 6 months follow-up, 21 patients are needed to improve median PFS from 2 months to 4 months or HR = 0.5 with 80% power using a two-sided one sample log-rank test at the 0.05 level of significance. Time to progression was assumed to follow an exponential distribution.

For the HCC cohort, the median PFS in the KEYNOTE-224 trial (Zhu et al. 2018) is 4.9 months. Assuming an accrual time of 12 months and 10 months follow-up, 24 patients are needed to improve median PFS from 4.9 months to 10 months or HR = 0.49 with 80% power using a two-sided one sample log-rank test at the 0.05 level of significance. Time to progression was assumed to follow an exponential distribution.

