9.3 Data Analyses/Study Endpoints

9.3.1 Efficacy Analysis

The primary analysis will be based on an intention to treat approach and will include all subjects entered into the study at Cycle 1 Day 1.

The primary efficacy endpoint will be Progression-Free Survival. For each cohort, the logrank test will be used to test the null hypothesis that the median PFS is less than or equal to 2 months for the AGC cohort and 4.9 months for the HCC cohort under exponential distribution assumption for time to progression. If this assumption is violated, bootstrap methods will be used to construct a 95% confident interval for the median.

Kaplan-Meir (KM) curves with 95% confidence bands will be constructed for PFS of each cohort. For the secondary endpoints, exact 95% confidence intervals for ORR, DCR will be constructed and KM curves for OS will be reported. For the exploratory objectives, 95% confidence intervals for change in mean values of biomarkers such as inflammatory cytokines, plasma metabolites will be constructed.

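### The one-sample log-rank test that reproduces n = 21 and n = 24 runs at about 1.6% in the benefit direction and 4% in the harm direction, so 9.3.1 should name the statistic and set a calibrated benefit-side cutoff

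*Combined protocol and SAP*

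**What the plan says.** Section 9.1 plans each cohort "using a two-sided one sample log-rank test at the 0.05 level of significance", under an exponential assumption. For AGC it states that "21 patients are needed to improve median PFS from 2 months to 4 months or HR = 0.5", with 80% power. For HCC it states that "24 patients are needed to improve median PFS from 4.9 months to 10 months or HR = 0.49", also with 80% power. The time assumptions are 12 months' accrual in both cohorts, with 6 months' follow-up for AGC and 10 for HCC.

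Section 9.3.1 gives the test a direction: "the logrank test will be used to test the null hypothesis that the median PFS is less than or equal to 2 months" in AGC, and the same with 4.9 months in HCC. It calls the test only the log-rank test. Neither section gives the variance of the statistic, a critical value, or a rule for declaring benefit.

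**The concern.** The one-sample log-rank statistic compares observed events O with the number E expected under the benchmark hazard. Several variances are in use, and with about 20 patients they do not behave alike. The standard form divides by √E. Because E grows with follow-up time and moves with O, the statistic is skewed in small samples, and a symmetric ±1.96 cutoff does not put 2.5% in each tail.

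Two things are at stake. The stated two-sided 0.05 level may not be what the test delivers, and the one direction that 9.3.1 asks about may be tested at a level other than 2.5%. Also, if the variance is left open, the choice between two common forms could be made after the data are seen. In a result near the threshold they can disagree.

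**Working it through.** **Inputs (all from 9.1).** AGC: null median 2.0 months, alternative 4, n = 21, accrual A = 12, follow-up F = 6. HCC: 4.9, 10, n = 24, A = 12, F = 10. Two-sided 0.05, power 80%, exponential times. Uniform accrual is my assumption. No dropout rate is stated, so the base case is none.

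**Step 1: reproduce the sample sizes.** With λ0 = ln2/null median and λ1 = ln2/alternative median, the per-patient expectations under the alternative are

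- p1 = E[O] = 1 − (e^(−λ1F) − e^(−λ1(F+A)))/(λ1A)
- p0 = E[E] = (λ0/λ1)·p1
- s1² = Var(O−E) = p1 + λ0²E[X²] − 2λ0E[O·X] − (p1−p0)², where X is time at risk.

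For the standard variance, n = (1.960√p0 + 0.8416·s1)²/(p0−p1)².

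| | p1 | p0 | s1² | n |
|---|---|---|---|---|
| AGC | 0.8512 | 1.7025 | 2.4945 | (2.557 + 1.329)²/0.8512² = 20.85 → 21 |
| HCC | 0.6605 | 1.3480 | 1.4768 | (2.276 + 1.023)²/0.6875² = 23.02 → 24 |

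Both stated sizes are matched, with formula power 80.3% and 81.6%. Other forms do not give both: variance (O+E)/2 gives 18 and 19, one-sided 0.05 gives 17 and 19, a log-hazard-ratio formula gives 20 and 24, and a Poisson formula gives 16 and 19. The standard variance is therefore a well-supported inference about the sizing, though the text does not state it.

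**Step 2: tails and power at cutoff 1.96.** Simulation with 1,000,000 trials per scenario, O = events, E = λ0 × total time at risk:

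| | Benefit tail | Harm tail | Total | Power |
|---|---|---|---|---|
| AGC, (O−E)/√E | 1.6% | 4.0% | 5.6% | 83.8% |
| AGC, (O−E)/√((O+E)/2) | 2.5% | 2.3% | 4.9% | 87.5% |
| HCC, (O−E)/√E | 1.6% | 3.9% | 5.5% | 84.5% |
| HCC, (O−E)/√((O+E)/2) | 2.6% | 2.3% | 5.0% | 88.4% |

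Rows may differ from their sums by rounding. Repeat runs agree to about 0.1 point; the HCC benefit tail of the modified form came out at 2.6 to 2.7%.

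**Step 3: calibrate both forms to a 2.5% benefit tail.** The standard form needs a cutoff of about −1.79 (AGC) and −1.81 (HCC). The modified form needs about −1.96 (AGC) and −1.98 to −1.99 (HCC). Power is then the same for both forms: about 87.5% in AGC and 88% in HCC.

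**Step 4: sensitivity to dropout (assumed 10% and 20% per year).** The standard form's tails stay at 1.5 to 1.7% and 3.8 to 4.1%. At 20% its power is 81.5% (AGC) and 80.0% (HCC); calibrated, it is 85.6% and 84.3%.

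**The case against.** The strongest reply is that the plan delivers what it promises. It states 80% power, and the standard test gives about 84% without dropout and still about 80% or more with an assumed 20% annual dropout. A reader might infer that the trial loses planned power; the documents do not support that, since any shortfall is relative to a different cutoff and not to the plan. This part of the reply stands.

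A reader might also infer from the 5.5 to 5.6% total that the efficacy claim carries inflated error. It does not. The null in 9.3.1 is directional and the excess lies in the harm tail, which cannot lead to a claim of benefit. In the direction that matters the test is conservative.

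Nor is the modified variance a free gain. All of the extra power comes from letting the benefit-side error rise from about 1.6% to 2.5%; at equal benefit-side error the two statistics have the same power (step 3). At 1.96 the modified form in HCC even sits slightly above 2.5%. Some would prefer a conservative test in a single-arm comparison with a historical benchmark, and that preference is defensible if it is stated.

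Finally, these tail figures assume exact event times. Section 6.2.3 allows imaging per standard of care or every 9 weeks, about 2.07 months, which is longer than the AGC null median. If progression were dated only at 9-week scans and the benchmark medians were true-time medians (an assumption; the documents do not give the benchmarks' scan schedules), the standard test's null benefit tail would be about 28% in AGC and 7% in HCC. That would dwarf a one-point tail difference, and calibration under exact times would not cure it.

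What remains is that the level is stated as two-sided 0.05 with no variance or cutoff, and the statistic implied by the sample sizes does not deliver it.

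**Conclusion.** The point holds as a cheap improvement and does not undermine the design. With the statistic that reproduces both sample sizes, the stated two-sided 0.05 is about 5.5 to 5.6%, split about 1.6% benefit and 4% harm, and the only direction under test runs below its nominal 2.5%. A calibrated benefit-side cutoff brings that error to 2.5% and adds about 3.5 points of power at the same N (about 84% to 87.5% in AGC and 88% in HCC).

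This rests on the standard variance being carried from sizing into analysis, which the text leaves open, and on exponential PFS, uniform 12-month accrual, 6 or 10 months' follow-up, no dropout and exact event times. The tail split is stable under 10 to 20% annual dropout. If HCC were analysed after only 6 months' follow-up, the power of the standard form at 1.96 would be 78.4%, and 82.9% with a calibrated cutoff.

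**What to change.** Before any analysis of PFS, amend 9.3.1 to (a) name the statistic, (b) declare success only in the benefit direction at one-sided 0.025, and (c) use an exact or simulated critical value for the stated design. For (O−E)/√E this is about −1.79 in AGC and −1.81 in HCC. The form (O−E)/√((O+E)/2) is an acceptable alternative; its AGC cutoff can stay at −1.96, but the HCC cutoff should be calibrated to about −1.99. Match 9.1 to the same statistic, direction and cutoff, and restate the power. If the actual accrual pattern or data cut differs from plan, recompute the cutoff from entry dates and cut date alone, without using outcomes.

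The cost is about one sentence in each of 9.1 and 9.3.1 and a short simulation, with no added patients, visits or data. The downside to record is that the benefit-side false-positive rate rises from about 1.6% to the nominal 2.5%. If the sponsor prefers to keep the conservative 1.96 cutoff, naming the statistic and stating its actual benefit-side level would at least fix the rule in advance.
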